#### **4.5.1.2 Presentation**

##### **Overall overview**

An AE overview table will be created, with AEs falling within the following categories summarized by treatment group.

- Any AE
- Any SAE
- Any AE with outcome death
- Any AE leading to discontinuation of IP
- Any AE possibly related to IP
- Any event of hypokalaemia
- Any event of hyperkalemia requiring rescue therapy

This summary will be replicated for on-treatment analysis period.

##### **AEs, SAEs, DAEs and deaths, by system organ class and preferred term**

A detailed overview of number, and percentage, of subjects with AEs, SAEs, DAEs and deaths in a particular SOC and PT class will be presented. In addition, for AEs and SAEs, a corresponding overview of the number of AEs in a particular SOC/PT class, and the rate of AEs, will be created.

The summaries of SAEs and DAEs will be replicated for on-treatment analysis period.

##### **Most common AEs**

A tabulation of the PT terms for most common AEs, i.e. AE PT terms that occur in more than 10% of the patient population (both treatment arms combined), will be provided. It will be replicated for the on-treatment study period.

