### **4.5 Safety Analyses**

The domain safety covers adverse events, clinical laboratory, vital signs, and ECG.

Tables and listings are, as a rule, provided for the SS, except for an SAE listing that displays SAEs for non-randomised subjects that occur during screening.

The primary method for presentation of summary of safety will be “during the study” (see Section 3.3.1.4 for the definition of this time period), reflecting the ITT approach used for the efficacy analyses. However, a selection of tabulations will be replicated for “on treatment” period, as supportive information.

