### **Causality of AEs**

Number and percentage of subjects with AEs considered as possibly related to IP will be tabulated by SOC and PT.

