### **Events of special interest: oedema, hypokalemia and hyperkalemia**

An overview of oedema-related AEs, with number and percentage of subjects with an event with a particular PT term, will be presented.

Number of subjects with AE classified as hypokalemia, or hyperkalemia requiring rescue, will be tabulated in a similar manner.

Both of these overviews, oedema-related AEs and hypo-hyperkalemia AEs, will be replicated for the on-treatment period as well as during study.

**Dialysis adequacy (Kt/V)** as a continuous variable will be summarized descriptively as described in Section 3.3.

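### The common-AE table picks terms by pooled frequency, so a reaction concentrated in one arm can drop out of the only general on-treatment display of non-serious AEs (minor)

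*SAP*

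**What the plan says.** SAP 4.5 makes the during-study period the primary basis for safety and describes the on-treatment period as supportive: "However, a selection of tabulations will be replicated for" it. SAP 4.5.1.2 then sets out the AE outputs.

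- **Most common AEs.** The table covers "AE PT terms that occur in more than 10% of the patient population (both treatment arms combined"). Of its on-treatment version the SAP says "It will be replicated for the on-treatment study period".
- **SOC/PT tables.** Numbers and percentages of "subjects with AEs, SAEs, DAEs and deaths in a particular SOC and PT class will be presented", with no frequency threshold. The on-treatment repeat is narrower: "The summaries of SAEs and DAEs will be replicated for on-treatment analysis period". The all-AE table is not named there.
- **Overall overview.** Counts by category of AE, not by PT: "This summary will be replicated for on-treatment analysis period".
- **Events of special interest.** "Both of these overviews, oedema-related AEs and hypo-hyperkalemia AEs, will be replicated for the on-treatment period as well as during study".
- **Causality.** "Number and percentage of subjects with AEs considered as possibly related to IP will be tabulated by SOC and PT". No on-treatment version is stated for this table or for the intensity table.
- **Listings.** All AEs are listed for the during-study period, with time since the last actual dose.

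**The concern.** The safety objective (Protocol Section 3, Table 3) is comparative: safety and tolerability of SZC against placebo. A table meant to help that comparison should not select its rows in a way that disfavours terms on which the arms differ. A pooled cut-off does so. For a given frequency on SZC, the lower the frequency on placebo, the less likely the term is to appear. Background events of dialysis, similar in both arms, pass easily.

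For the during-study period this affects only a convenience summary, because the full SOC/PT table sits beside it. On treatment there is no full all-AE table. The two periods can also differ materially. Participants who stop study intervention are followed to study closure where possible (Protocol 7.1.4), the anticipated average treatment period is about 37 months, and the on-treatment period ends one day after the last actual dose (SAP 3.4.1.4). At stake is whether a reader of the on-treatment tables would see a non-serious, tolerated reaction that separates the arms.

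**Working it through.** The 10% cut-off is a reporting choice, so the plan has no derived figure to reproduce. Two checks apply: what the rule excludes, and which other on-treatment tables would show an excluded term.

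**1. What the rule excludes**

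Inputs: 1:1 allocation and about 2800 randomised (Protocol 9.2; SAP 3.3), which is 5600 × (1 − 0.50) = 2800, or 1400 per arm. The Safety Set requires at least one dose; I assume it is close to 1400 per arm. The documents give no AE rates, so the rates below are illustrative.

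Let a and b be the arm proportions. With equal arms the pooled proportion is (a + b)/2, and a term is shown only if (a + b)/2 > 0.10, that is a + b > 0.20. At 1400 per arm this means more than 280 participants in total. The largest SZC count still omitted is 280 minus the placebo count:

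- placebo 0%: 280/1400 = 20%
- placebo 1% (14): 266/1400 = 19%
- placebo 4% (56): 224/1400 = 16%
- placebo 5% (70): 210/1400 = 15%

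The 20% ceiling follows from equal allocation and does not depend on the number of participants.

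The 95% CI for the risk difference is (a − b) ± 1.96 × √[a(1 − a)/1400 + b(1 − b)/1400].

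| SZC v placebo | Counts | Pooled | Shown, pooled rule | Shown, either-arm rule | Difference in points (95% CI) |
|---|---|---|---|---|---|
| 20% v 0% | 280 v 0 | 10.0% | No | Yes | 20 (17.9 to 22.1) |
| 15% v 4% | 210 v 56 | 9.5% | No | Yes | 11 (8.9 to 13.1) |
| 12% v 6% | 168 v 84 | 9.0% | No | Yes | 6 (3.9 to 8.1) |
| 11% v 11% | 154 v 154 | 11.0% | Yes | Yes | 0 |
| 10% v 2% | 140 v 28 | 6.0% | No | No | 8 (6.3 to 9.7) |
| 6% v 2% | 84 v 28 | 4.0% | No | No | 4 (2.6 to 5.4) |

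The first row is omitted because the rule requires more than 10%, and the pooled value is exactly 10%. The last two rows show that an either-arm rule at 10% does not recover everything.

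**2. Which on-treatment tables would show an excluded term**

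| On-treatment output | By PT? | Non-serious AEs covered |
|---|---|---|
| Overall overview | No | Counted by category only |
| SAEs by SOC/PT | Yes | None |
| AEs leading to discontinuation, by SOC/PT | Yes | Only those that led to discontinuation |
| Oedema, hypokalemia and hyperkalemia overviews | Oedema by PT; potassium events by class | Only those events |
| Most common AEs | Yes | All, subject to the pooled 10% filter |

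A non-serious AE that did not lead to discontinuation and is not an oedema or potassium event therefore has one on-treatment PT table, the filtered one.

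**3. A point left open**

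The SAP does not say whether the on-treatment table applies the 10% rule afresh to on-treatment events or keeps the terms selected for the during-study period.

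**The case against.** The strongest reply is that nothing goes unreported. The during-study period is primary, and for it the SAP gives every AE by SOC and PT with no threshold, with event counts and rates, plus intensity and causality tables. Protocol 9.4.3 asks for AEs by SOC/PT, intensity and causality; the SAP delivers each, and the Protocol does not ask for a common-AE table at all. By the definitions in SAP 3.4.1.4 the on-treatment period lies essentially within the during-study period, so a term at 15% v 4% on treatment would appear in the unfiltered table at no less than those percentages. The all-AE listing carries time since last dose. The risks identified for SZC, hypokalemia and oedema-related events (Protocol 2.3), have their own unfiltered on-treatment overviews. Safety is descriptive, so no test or decision turns on which rows are printed. A pooled cut-off is also a transparent, arm-neutral meaning of common.

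Most of this stands, and it rules out two stronger readings. A reader might infer that a drug-specific harm could vanish from the safety report; the unfiltered during-study table and the listing exclude that. A reader might also infer that an excluded non-serious AE would be missing from every on-treatment PT table. That is too broad, because the table of AEs leading to discontinuation has no threshold and includes non-serious events.

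The reply does not remove the gap in the on-treatment view. The during-study table mixes events on and off drug, so it does not stand in for an on-treatment comparison, and rebuilding one from listings is work the tables are meant to spare the reader. The SAP chose to give an on-treatment common-AE table, and its selection rule works against the terms that would make the table informative.

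**Conclusion.** The point holds in a limited form and is minor. The pooled rule omits a term with up to 20% in one arm and 0% in the other, and shows a balanced term at 11%. The consequence is confined to the common-AE summary and, on treatment, to non-serious AEs that did not lead to discontinuation and are not oedema or potassium events. An arm-separating reaction of that kind can be missing from the supportive on-treatment tables by PT, though not from the report.

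This rests on near-equal arms in the Safety Set and on reading the SAP's list of on-treatment repeats as complete. SAP 4.5 speaks only of a selection of tabulations, so the sponsor may intend more than 4.5.1.2 names. The example rates show how the rule behaves; they do not predict AE frequencies in this trial.

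**What to change.** In SAP 4.5.1.2, Most common AEs, replace the pooled criterion with: more than 10% of subjects in either treatment arm. Use it in both the during-study and the on-treatment version, and state that it is applied to the events of the respective period.

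This is a partial fix, because terms at or below 10% in both arms (10% v 2%, for example) remain out. To close the rest, add the all-AE SOC/PT table to the SAE and discontinuation tables already repeated on treatment.

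The criterion change costs one phrase and a few more rows. It can also admit a term that is just above 10% in one arm by chance, which is tolerable in a descriptive table. The second change adds one on-treatment run of a table already planned. Neither touches an efficacy analysis or the type I error.

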### **Intensity of AEs**

An overview of the number and the percentage of subjects with AEs in a particular SOC, PT and intensity class (mild, moderate, severe) will be created. Subjects will be counted only once in each category. A subject with two AE in the same SOC and PT class of e.g. both high and moderate intensity will be assigned the “high” intensity category, i.e. the more severe class.

### **Causality of AEs**

Number and percentage of subjects with AEs considered as possibly related to IP will be tabulated by SOC and PT.

### **Events of special interest: oedema, hypokalemia and hyperkalemia**

An overview of oedema-related AEs, with number and percentage of subjects with an event with a particular PT term, will be presented.

Number of subjects with AE classified as hypokalemia, or hyperkalemia requiring rescue, will be tabulated in a similar manner.

Both of these overviews, oedema-related AEs and hypo-hyperkalemia AEs, will be replicated for the on-treatment period as well as during study.

**Dialysis adequacy (Kt/V)** as a continuous variable will be summarized descriptively as described in Section 3.3.

### **Key subject information tables**

Key subject information will be provided for all SAEs, AEs with an outcome of death, and all AEs leading to IP discontinuation. This will include e.g. the duration variables defined in the beginning of this section, outcome of an AE and action taken with respect to IP.

### **Listings**

The listings provided will include, but may not be limited to:

- All AE
- All AE of hypokalemia. The listing will e.g. include information on the actual SK value observed during the AE.
- SAE for enrolled, but not randomized, subjects.

All listings will be created for during the study time period, and will include planned treatment arm, actual treatment arm, planned dose, actual dose and time since the actual last IP administration date.

#### **4.5.2 Clinical Laboratory, Vital Signs and ECG**

Blood samples will be taken at Visit 1, 2, 3, 4 (randomization), and 8 (12-month) for the determination of clinical chemistry by a central laboratory; a full list of the laboratory variables for this study is provided in Table 7 of the CSP. For the definition of baseline, see Section 3.3.1.5.

Vital signs (pulse and BP) will be assessed at Visit 1, 4 (randomization) and end of study intervention visit (EOIV) or premature study intervention discontinuation visit (PIDV).

A 12-lead ECG will be performed at Visit 1 and 4 (randomization). That is, only the baseline ECG value will be available for this study.

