**Table 2 Schedule of Activities – Randomized Study Intervention Phase**

Visit Description	Randomization On-site Visit	3 months On-site Visit	6 months On-site Visit	9 months On-site Visit	12 months On-site Visit	TC/Video/ On-site Visit a	EOIV or PIDV On-site Visit	SCV TC/Video/ On-site Visit a	Details in CSP Section or Appendix
Visit	4	5	6	7	8	9, 10, 11, etc.	EOIV or PIDV b	SCV c	
Study Day	1	92 ± 7 days	183 ± 7 days	274 ± 7 days	365 ± 7 days	Every 3 rd Month ± 7 days			
Type of Visit	LIDI	LIDI	LIDI	LIDI	LIDI	LIDI	LIDI	LIDI	
Study Events evaluation/ Study Events Questionnaire h	X	X	X	X	X	X	X	X	Appendix B 5
Concomitant medication	X	X	X	X	X	X	X	X	Section 6.5
Endpoint collection f	X	X	X	X	X	X	X	X	Section 8.1
AEs and SAEs	X	X	X	X	X	X	X	X	Section 8.3

a Visit can be done via TC, video call or on-site visit, if more convenient.

b Refer to Section [7.1.5](#) for further details on the EOIV. Refer to Sections [7.1](#) and [7.1.4](#) for further details on the PIDV. The PIDV is not required to be performed at a LIDI visit.

c Refer to Section [7.1.6](#) for further details on the SCV.

d Pulse and BP should be measured in triplicate after the participant is comfortably at rest in either supine or seated position quietly for at least 5 minutes.

e The prior session post-dialysis weight measured at dialysis session immediately prior to the study visit will be used in the calculation of interdialytic weight gain.

f Potential endpoints will be collected from randomization throughout the study until and including the participant's last visit.

g Pre and post-dialysis weight not to be collected if the visit is done via TC/ video.

h Study Events evaluation to be done during study intervention dispensation visit. Study Events Questionnaire to be used to facilitate the evaluation. In case Study Events evaluation is not done by the Investigator/ Sub-investigator and there is positive answer to any of the question unscheduled follow up visit/ phone visit should be done by Investigator/ Sub-investigator within a week to complete Study Event evaluation and to report AEs. In case an SAE needs to be reported, timelines for SAE reporting apply.

Refer to Appendix [B 5](#) Study Events Questionnaire.

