### **7.1.4      Procedures for Premature Study Intervention Discontinuation Visit**

The investigator should instruct the participant to contact the site before or at the time study intervention is stopped. Participants who prematurely and permanently discontinue study intervention should return for a PIDV, which should be performed at the earliest possible dialysis visit after the last dose of study intervention. See the SoA (Section 1.3) for assessments to be performed at the PIDV.

A participant who decides to discontinue study intervention will always be asked about the reason(s). The date of last dose of study intervention should be documented in the eCRF, as well as the date of study intervention discontinuation. All study intervention should be returned by the participant, and drug accountability should be checked and documented in the eCRF.

Discontinuation of study intervention, for any reason, does not impact on the participant's participation in the study. The participant should, if possible, continue attending subsequent study visits, including the SCV, and data collection should continue according to the study protocol. If, upon discontinuation of study intervention, the participant chooses to withdraw from the study entirely, procedures described in Section 7.2 should be followed.

Data collection and procedures should continue according to the study protocol until study closure. If the participant does not agree to this option (which must be documented), a modified follow-up (eg, regular telephone contacts or a contact at study closure) should be arranged, if agreed to by the participant and in compliance with local data privacy laws/practices in order to collect at least the study endpoint information. If the participant does not allow the site to call him/her but allows the site to review the participant's medical records it should be done following the protocol-specified visit schedule or at least every 6 months until the study closure, to ensure collection of study endpoint information.

After stopping study intervention, the investigator should ensure that the participant is treated according to standard clinical practice and ascertain there is a proper medical follow-up plan in place.

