### **7.1.5 Procedures for End of Study Intervention Visit**

All participants who are still on study intervention at the SED will be asked to return for an EOIV, which should be performed at the earliest possible LIDI dialysis visit but no later than 3 weeks after the SED. At this visit the participant will be taken off the study intervention. See the SoA (Section 1.3) for assessments to be performed at the EOIV.

The date of last dose of study intervention should be documented in the eCRF. All study intervention should be returned by the participant, and drug accountability should be checked and documented in the eCRF.

After stopping study intervention, the investigator should ensure that the participant is treated according to standard clinical practice and ascertain there is a proper medical follow-up plan in place.

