##### **On-treatment**

“On-treatment” is defined as the period between the first day of planned intake of study intervention to one day after the day of the last actual dose of study intervention.

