##### **4.5.2.2 Presentations**

###### **Summary of measurements over time**

The result and the change from baseline of each clinical chemistry and vital sign variable will be summarized, by treatment group, at baseline and 12-month visit (for labs) or EOIV/PIDV (for vital signs), using descriptive statistics as appropriate for continuous variables. For the ECG variables, only the baseline measurements will be presented, with no change from baseline, as there are no planned post-baseline ECG measurement occasions. The absolute values, as well as the changes, will also be illustrated by means of box plots.

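### The SAP says no post-baseline ECG is planned, but the protocol schedules one at the end-of-intervention or premature-discontinuation visit, so it goes unsummarised

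*SAP*

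**What the plan says.** SAP 4.5.2 gives Visit 1 and Visit 4 as the only ECG occasions and concludes that "only the baseline ECG value will be available for this study". SAP 4.5.2.2 (Summary of measurements over time) presents ECG variables at baseline without change from baseline, "as there are no planned post-baseline ECG measurement occasions". Yet SAP 4.5 counts ECG as part of safety: "The domain safety covers adverse events, clinical laboratory, vital signs, and ECG".

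The protocol's schedule differs. Table 1 has an ECG at Visit 1. Table 2 has one at randomization (Visit 4) and one in the column for EOIV or PIDV. Protocol 8.2.4 ties ECG timing to the schedule of activities and requires ECG data, with QTcF, in the eCRF. Protocol 7.1.5 says of the EOIV: "See the SoA (Section 1.3) for assessments to be performed at the EOIV". Protocol 7.1.4 makes the same reference for the PIDV.

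**The concern.** The SAP's only stated reason for leaving out post-baseline ECG results contradicts the protocol. It is not a declared change: SAP Section 2 reports no departures from the protocol's planned analyses apart from renaming the safety set, and neither document's amendment history records removal of the EOIV/PIDV ECG.

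At stake is a descriptive safety summary. The trial studies arrhythmia outcomes under a potassium-lowering drug. Protocol 2.3 names hypokalemia as an identified risk, and Protocol 7.1.1 has a QTc criterion for stopping study intervention, part of which is defined by change from baseline. That is the quantity the SAP declines to present. Followed as written, the study report would show no post-baseline ECG or QTcF values by arm and would say, incorrectly, that none were planned.

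**Working it through.** No power or alpha figure is involved. The check is a comparison of the two schedules.

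**1. Reading Protocol Table 2.** The visit columns, in order, are:

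1. Visit 4 (randomization)
2. Visit 5
3. Visit 6
4. Visit 7
5. Visit 8 (12 months)
6. Visits 9 onward
7. EOIV or PIDV
8. Study closure visit (SCV)

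The ECG row is marked in columns 1 and 7 and blank in 2 to 6 and 8.

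**2. Confirming the column count.** Two other rows support this reading.

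- Pre-dialysis weight has seven consecutive marks and a blank eighth cell, so column 7 is EOIV/PIDV and column 8 is SCV.
- Pulse and blood pressure has exactly the ECG pattern. SAP 4.5.2 reads that row, with Table 1, as "Visit 1, 4 (randomization) and end of study intervention visit (EOIV) or premature study intervention discontinuation visit (PIDV"). The next statement in the same SAP section reads the identical ECG pattern without EOIV/PIDV.

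**3. Counting occasions.**

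| Occasion | Protocol | SAP 4.5.2 | Period |
|---|---|---|---|
| Visit 1 | yes | yes | baseline |
| Visit 4 | yes | yes | baseline |
| EOIV or PIDV | yes | no | post-baseline |
| Total | 3 | 2 | |
| Post-baseline | 1 | 0 | |

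Visits 1 and 4 both belong to baseline because SAP 3.4.1.5 takes the last value on or before the randomization date. The EOIV/PIDV ECG is therefore the only scheduled one from which a change can be calculated.

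**4. Looking for another output that would show it.** The abnormality tables in SAP 4.5.2.2 cover haematology, clinical chemistry and vital signs. The listings it names cover laboratory and vital-sign abnormalities. No specified output contains a post-baseline ECG or QTcF value.

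**5. How many ECGs.** EOIV is for participants still on intervention at the study end date; PIDV is for those who stopped permanently before it. Each participant thus has at most one, and the ceiling is 2800 × 1 = 2800. The documents give no rates of death, withdrawal or missed visits, so the number obtained cannot be derived.

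**6. Would these ECGs reflect treatment?** SAP 3.4.1.4 ends the on-treatment period "one day after the day of the last actual dose of study intervention".

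- The EOIV takes place at a dialysis visit after the long interdialytic interval (LIDI), in participants still on intervention who dose on non-dialysis days. For an adherent participant the last dose would usually be the day before, inside the window.
- The PIDV is a visit "which should be performed at the earliest possible dialysis visit after the last dose of study intervention", and Table 2 footnote b adds: "The PIDV is not required to be performed at a LIDI visit". Its ECG may fall outside the window and at a different point in the dialysis cycle.

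The two visits should therefore not be pooled without distinction.

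**The case against.** The strongest objection is that nothing promised has been dropped. ECG is not among the protocol's safety endpoints. Protocol 9.4.3 names laboratory data, vital signs and interdialytic weight gain for tabulation and leaves full details to the SAP. This stands: the sponsor may choose not to summarise these ECGs, but it needs a true reason, and the one given is false.

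The important QT signals also have other routes. A QTc-triggered stop would appear in disposition, and in the tables of adverse events leading to discontinuation if reported as an adverse event. Staying on drug after meeting a stopping criterion is an important protocol deviation category in SAP 3.4.4. Arrhythmia events are adjudicated. This also stands and limits the consequence, but none of these routes compares QTcF between arms.

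The Table 2 evidence can be questioned too. In the text copy used here, the central laboratory row has one mark, under Visits 9 onward, which cannot be right and must be an extraction fault. The ECG row shows no such displacement and is corroborated by the weight and pulse rows and by the SAP's own reading of the latter.

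Finally, the CRF is not available, so the origin of the SAP statement is not proven and capture of the ECG at EOIV/PIDV rests on Protocol 8.2.4. The SAP's listings are open-ended, so an ECG listing is not excluded; it is not promised either.

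**Conclusion.** The concern holds. SAP 4.5.2 and 4.5.2.2 are wrong about the protocol's ECG schedule, most likely through a slip in transcribing Table 2. As written, they leave the only scheduled post-baseline ECG, at most one per participant and at most 2800 in all, without a summary by arm.

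The gap is confined to descriptive safety reporting. Adverse event tables, adjudicated events, the primary analysis, power and alpha are unaffected. It should still be corrected, because the stated premise is false and the repair is small. The conclusion rests on the ECG row of Table 2 as read above, and on the eCRF capturing the ECG as Protocol 8.2.4 requires.

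**What to change.** **Needed**

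- In SAP 4.5.2, give the ECG schedule as Visit 1, Visit 4 and EOIV or PIDV. Remove the statement there that only baseline ECG values will exist, and the statement in 4.5.2.2 that no later ECG is planned.
- Add descriptive by-arm summaries of the ECG variables, including QTcF, with change from baseline. If the sponsor prefers to omit them, give a correct reason and record it in SAP Section 2.

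**Useful additions**

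- Show EOIV and PIDV separately and flag on-treatment status under SAP 3.4.1.4.
- Tabulate by arm the number of participants whose values meet the QTc criteria as worded in Protocol 7.1.1 (QTc above 550 msec; a rise of over 60 msec that takes it past 500 msec). Note that Appendix E adds an investigator-judgement criterion for Italy that these counts would not reproduce.
- Footnote that Protocol 8.2.4 does not fix ECG timing relative to dialysis.

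The cost is a few sentences of SAP text and a small number of descriptive tables. If the eCRF follows Protocol 8.2.4, no new procedure or data collection is needed.
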